### **11.4.3 Handling of missing values/censoring/discontinuations**

No imputation of missing data for dropouts will be done.

Corporate Confidential  
Information

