### **11.4.4 Supportive analyses**

In order to assess the robustness of the results, the primary analysis will be repeated on the FAS.

In addition, the changes from baseline in QMG scores at each visit of the treatment period (weeks 5, 9, 13, 17, 21 and 25) will be analyzed using a mixed effect model for repeated measurements. The model may investigate effects for treatment (CFZ533 or placebo), time (visit week), baseline QMG score, treatment by time and baseline by time interactions. An unstructured covariance matrix may be used to model the correlations between the measurements in the same subject. In case of convergence issues, the covariance matrix that best fit the data will be chosen. The estimated treatment differences at each visit will be provided with 90% CI and 2-sided p-values.

Other potentially influent factors such as sex, age at onset of the disease, makers of baseline severity of the disease or prednisone dose may be explored.

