The proportion of patients with improvement by  $\geq 3$  points in QMG score at Week 25, the proportion of patients with worsening by  $\geq 3$  points in QMG score at week 25, the proportion of patients intolerant to steroid taper and the proportion of patients who discontinued due to inefficacy or worsening before week 25 will be analyzed via logistic regression with treatment as a factor compared between CFZ533. Additional covariates such as sex, gender, age at onset of MG, QMG score at baseline will be explored. Odds ratios together with 90% CI and p-values will be provided for comparisons of CFZ533 versus placebo utilizing the logistic regression model fitted.

The statistical analysis for exploratory efficacy and PD variables will be described in the RAP.

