## 11.6 Sample size calculation

The sample size is based on the primary efficacy endpoint and the primary analysis described in [Section 11.4.2](#)

Corporate Confidential Information

A sample size of 36 evaluable patients (18 on CFZ533, 18 on placebo) was determined, assuming a SD of 5.5 ([Zinman et al 2007](#)) for the QMG endpoint. To account for approximately 20% anticipated dropouts, 44 patients will be randomized in this study (22 on CFZ533 and 22 on placebo).

To account for potential discontinuations due to non-detectable AChR or MuSK autoantibodies, the sample size might be increased to compensate the discontinued seronegative patients. The operating characteristics of this design are shown on [Figure 11-1](#) below. The probability of reaching the target efficacy (success) at final analysis is about 8% if CFZ533 is equal to placebo, and it is >80% if the true difference between CFZ533 and

placebo is  $\geq 4.5$ . At the planned IA the probability of success is 42% if the true difference between CFZ533 and placebo is  $\geq 4.5$  and the probability of stopping for futility is 5% if CFZ533 is equal to placebo. This sample size was considered adequate to preliminarily evaluate the efficacy of CFZ533 in the treatment of myasthenia gravis.

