7.1.5 Handling of missing values/censoring/discontinuations

No imputation of missing data dropouts or any other reason will be done. The main analysis model will include all data of all patients in the PD analysis set, including dropouts.

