7.2.3 Statistical model, assumptions and hypotheses

The changes from baseline in MGC scores at each visit of the treatment period (weeks 5, 9, 13, 17, 21 and 25) will be analyzed using a mixed effect model for repeated measurements. The model may investigate effects for treatment (CFZ533 or placebo), time (visit week), baseline MGC score, treatment by time and baseline by time interactions. An unstructured covariance matrix may be used to model the correlations between the measurements in the same subject. In case of convergence issues, the covariance matrix that best fit the data will be chosen. The estimated treatment differences at each visit will be provided with 90% CI and 2-sided p-values.

Other potentially influential factors such as sex, age at onset of the disease, markers of baseline severity of the disease or prednisone dose may be explored.

The changes from baseline in MG-ADL and MG QOL-15 at each visit until Week 25 will be analyzed using the main mixed model as described above for MGC.

The proportions of patients requiring rescue therapy between Week 1 and Week 25 (i.e. IV immunoglobulins or plasma exchange) will be summarized. Time to first rescue therapy will be described using Kaplan-Meier curves and compared between CFZ533 and placebo using the logrank test. In case of dropouts, the data will be censored at the last visit before or at Week 25.

The changes from baseline in MGC score at Week 25 will be analyzed using the Bayesian model described above.

The proportion of patients with improvement by ≥ 3 points in QMG score at Week 25, the proportion of patients with worsening by ≥ 3 points in QMG score at Week 25, the proportion of patients intolerant to steroid taper and the proportion of patients who discontinued due to inefficacy or worsening before Week 25 will be analyzed via logistic regression with treatment as a factor (and baseline value as a covariate if relevant) compared between CFZ533 and placebo. Additional covariates such as sex, gender, age at onset of MG, QMG score at baseline will be explored. Odds ratios together with 90% CI and p-values will be provided for comparisons of CFZ533 versus placebo utilizing the logistic regression model fitted.

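### The visible SAP text gives the Week 25 ≥3-point QMG endpoints no denominator and no status for patients rescued, or discontinued for inefficacy or worsening, before Week 25

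*SAP*

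**What the plan says.** SAP 7.2.3 fits a logistic regression with treatment as a factor to "The proportion of patients with improvement by ≥ 3 points in QMG score at Week 25" and to "the proportion of patients with worsening by ≥ 3 points in QMG score at Week 25", reporting odds ratios, 90% confidence intervals and p-values. Protocol 11.5.1 says the same: the endpoints "will be analyzed via logistic regression with treatment as a factor compared between CFZ533" (the sentence breaks off there). SAP 7.2.1 adds only the Day 1 baseline and that a fall in QMG is an improvement.

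The nearest missing-data rules are in SAP 7.1.5, "No imputation of missing data dropouts or any other reason will be done", and Protocol 11.4.3, "No imputation of missing data for dropouts will be done". Both stand under the primary variable, and 7.1.5 continues with the main analysis model on the PD analysis set. For time to first rescue, SAP 7.2.3 has its own rule: "In case of dropouts, the data will be censored at the last visit before or at Week 25". Protocol 11.4.4 adds a robustness check, "In order to assess the robustness of the results, the primary analysis will be repeated on the FAS", which does not reach these endpoints.

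Patients without an ordinary Week 25 score are foreseen:

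- Protocol 7.1 makes rescue and worsening to MGFA class IVb or V reasons to stop study treatment. Those who discontinue participation are asked back for the end-of-study visit where possible.
- Protocol 6.9 lets rescued patients stay in the study.
- SAP Table 5-1 (deviation M02) removes a patient from the PD set at a visit where cholinesterase inhibitors were taken too close to testing.
- Protocol 11.6 states: "To account for approximately 20% anticipated dropouts, 44 patients will be randomized in this study".

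**The concern.** A binary endpoint at a single visit needs a stated status for every patient in a stated set. Here the patients at issue are the treatment failures. Those whose disease worsened enough to leave are the ones the worsening endpoint should capture, and they are also among the likeliest to have no Week 25 score. Those who received IVIg or plasma exchange may have a lower score because of the rescue and not the study treatment.

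The repeated-measures QMG model can use a dropout's earlier visits. A logistic model at Week 25 cannot, so the handling rule decides who is counted. With about 22 patients per arm, a few patients change the odds ratio materially, and without a written rule the choice falls to the analyst.

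**Working it through.** **The plan's own figure.** 36 evaluable × 1.20 = 43.2, or 22 per arm after rounding 18 × 1.20 = 21.6 up, so 44 is reproduced (36 / 0.80 = 45). The loss allowed for is 44 − 36 = 8, or 8/44 = 18.2%.

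**What the visible text yields for each kind of patient.**

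| Patient | Status in 7.2.3 / 11.5.1 | Result if 7.1.5 is carried over |
|---|---|---|
| Left for inefficacy or worsening, no Week 25 score | none | absent from both endpoints |
| Rescued, Week 25 score ≥3 points lower | none | improved |
| M02 deviation at Week 25 | none (Table 5-1 excludes that visit) | absent from both endpoints |

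Carrying 7.1.5 over is a deduction; 7.2.3 does not state it.

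**Assumed counts.** From Protocol 11.6: SD 5.5 and a true difference of 4.5. Assumed: normal changes and a placebo mean change m of 0 to −2. Then P(improved) = Φ((−3 − m)/5.5) and P(worsened) = 1 − Φ((3 − m)/5.5), with m − 4.5 in place of m for CFZ533. Expected counts of 22 per arm, CFZ533 vs placebo:

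- m = 0: improved 13.4 vs 6.4; worsened 1.9 vs 6.4
- m = −1: improved 14.9 vs 7.9; worsened 1.3 vs 5.1
- m = −2: improved 16.2 vs 9.4; worsened 0.9 vs 4.0

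I use 15 vs 8 improved (m = −1) and 2 vs 6 worsened (m = 0). The odds ratio is the cross-product, with 90% CI exp(ln OR ± 1.645·SE) and SE = √(1/a + 1/b + 1/c + 1/d).

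**Worsening.** All 22 per arm known: 2/22 vs 6/22, OR = (2 × 16)/(20 × 6) = 0.27 (0.06–1.14). Now let 4 per arm have no Week 25 score. The last column counts those who left for worsening as worsened and leaves the other missing patients out.

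| Missing patients who left for worsening | Observed cases | Failures counted |
|---|---|---|
| 2 placebo | 2/18 vs 4/18: 0.44 | 2/18 vs 6/20: (2 × 14)/(16 × 6) = 0.29 |
| 3 placebo | 2/18 vs 3/18: 0.625 | 2/18 vs 6/21: (2 × 15)/(16 × 6) = 0.31 |
| 4 placebo | 2/18 vs 2/18: 1.00 (0.17–5.72) | 2/18 vs 6/22: (2 × 16)/(16 × 6) = 0.33 (0.08–1.44) |
| 1 in each arm | 1/18 vs 5/18: 0.15 (0.02–1.02) | 2/19 vs 6/19: (2 × 13)/(17 × 6) = 0.25 (0.06–1.11) |

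Observed cases run from 0.15 to 1.00; with failures counted, from 0.25 to 0.33. Every interval includes 1, so what moves is the point estimate.

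**Improvement.** All 22 per arm known: 15/22 vs 8/22, OR 3.75 (1.31–10.70). Suppose all 8 missing patients are treatment failures and are left out (CFZ533/placebo split):

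- 2/6: 15/20 vs 8/16, OR 3.00 (0.92–9.79)
- 4/4: 15/18 vs 8/18, OR 6.25 (1.70–22.94)
- 5/3: 15/17 vs 8/19, OR 10.31 (2.41–44.19)

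Counting them as not improved returns 3.75 each time. With no true effect (8/22 vs 8/22, OR 1.00), leaving 8 failures out gives 0.67 at 2/6, 1.00 at 4/4 and 1.50 at 6/2; each interval includes 1. If missingness is unrelated to response, about 12/18 vs 7/18 gives 3.14 (1.00–9.87), close to 3.75.

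**Rescue credited as improvement.** Two rescued placebo patients: 15/22 vs 10/22, OR 2.57 (0.92–7.21). Two rescued CFZ533 patients: 17/22 vs 8/22, OR 5.95 (1.96–18.05).

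**The case against.** The strongest reply is that we see only part of the plan. SAP 1.1 says this document is Module 3. Module 7 holds the table shells and Module 8 the derived-variable specifications, where a responder flag and its denominator could well sit. Text is also redacted after Protocol 11.4.3 and SAP 7.2.5, and Protocol 11.4.2, SAP 7.1.3 and Table 8-1 are not shown. This stands: the point concerns the visible Module 3 text, and whether rescued patients have a Week 25 QMG cannot be checked.

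Second, SAP 7.1.5 with the PD set suggests a default: observed cases in that set with a Week 25 score. That is a fair reading, but it produces the two results at issue and does not deal with a post-rescue score.

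Third, rescue and discontinuation for inefficacy or worsening have their own analyses in SAP 7.2.3. A reader might infer that the plan loses its treatment failures altogether; it does not. Reporting them separately is legitimate, but nothing links them to the ≥3-point endpoints.

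Fourth, 8 missing may be too many. Protocol 4 ties the 36 to completing the study, which runs 24 weeks beyond treatment, so fewer may lack a Week 25 score. The largest improvement odds ratios also require every missing patient to be a non-improver. Both limits stand.

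A reader might also infer, from the dropout rule for time to rescue, that the gap is confined to these two endpoints. That does not follow. A Kaplan-Meier analysis needs a censoring rule in any case, and steroid-taper intolerance also has no stated denominator.

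**Conclusion.** The gap is real in the visible text and is more than missing detail. The only visible rule, if carried over, removes patients who left for worsening from the worsening endpoint and can credit rescue as improvement. The effect on the odds ratio can go in either direction. In the illustration the worsening estimate runs from 0.15 to 1.00 around a full-data value of 0.27, and crediting two rescued patients moves the improvement estimate from 3.75 to 2.57 or 5.95. These sizes rest on assumed response rates, up to about 8 of 44 missing as a planning allowance, and chosen splits of who is missing. They show sensitivity and are not a forecast.

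A reader might infer that the plan favours CFZ533, or that the trial's success criterion is compromised. The documents support neither. The direction depends on which arm the failures fall in. These are secondary endpoints in a non-confirmatory study, and the target-efficacy rule in the synopsis does not use them.

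**What to change.** Amend SAP 7.2.3 before database lock:

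1. Name the analysis set for both endpoints.
2. Count rescue (IVIg or plasma exchange) or discontinuation for inefficacy or worsening before Week 25 as not improved and as worsened, whatever the later score. Say that this takes precedence over 7.1.5 for these endpoints.
3. Keep the M02 visit-level exclusion of Table 5-1. Report by arm how many patients have no Week 25 score for other reasons.
4. Keep the observed-case analysis of both endpoints as a sensitivity analysis.

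If Module 7, Module 8 or redacted text already holds such a rule, a cross-reference in 7.2.3 is enough.

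The cost is a few lines of SAP text and one derived flag from rescue and discontinuation records that the plan already needs for its other endpoints. The downside is that both endpoints become composites with treatment failure and overlap the separate rescue and discontinuation endpoints, so the report should say so. Nothing changes in patient management or data collection.

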7.2.4 Model checking procedures

In case of convergence issues, the covariance matrix that best fit the data will be chosen.

Diagnostic plots will be provided.

7.2.5 Graphical presentation of results

Arithmetic mean (\pm SD) of secondary variables (MGC, MG-ADL, MG QOL-15, CD40 on B cells and total soluble CD40 in plasma) and their change from baseline will be plotted across time.

The proportion of patients requiring rescue therapy, the proportion of patients with improvement by ≥ 3 points in QMG score, the proportion of patients with worsening by ≥ 3

points in QMG score, the proportion of patients intolerant to steroid taper and the proportion of patients who discontinued due to inefficacy or worsening will be shown via bar charts.

Corporate Confidential Information

8 Statistical methods for safety and tolerability data

8.1.1 Variables

Adverse events, serious adverse events (SAEs), vital signs (blood pressure, pulse rate, body temperature), ECG intervals, laboratory measurements, immunogenicity, as well as subject demographics, baseline characteristics, and treatment information.

8.1.2 Descriptive analyses

All safety analyses will be performed on the safety analysis set; patients will be analyzed as treated.

Subject demographics and other baseline characteristics

All data for background and demographic variables will be listed by treatment group and subject. Summary statistics will be provided by treatment group.

Relevant medical history, current medical conditions, results of laboratory screens, drug tests and any other relevant information will be listed by treatment group and subject.

Treatment

Data for study drug administration, rescue medication and concomitant therapies will be listed by treatment group and subject.

Vital signs

All vital signs data will be listed by treatment, subject, and visit/time and if ranges are available abnormalities (and relevant orthostatic changes) will be flagged. Summary statistics will be provided by treatment and visit/time.

ECG evaluations

All ECG data will be listed by treatment, subject and visit/time, abnormalities will be flagged. Summary statistics will be provided by treatment and visit/time.

Clinical laboratory evaluations

All laboratory data will be listed by treatment, subject, and visit/time and if normal ranges are available abnormalities will be flagged. A separate listing is provided presenting all parameters in a subject with any abnormal values. Summary statistics will be provided by treatment and visit/time.

Adverse events

All information obtained on adverse events will be displayed by treatment and subject.

The number and percentage of subjects with adverse events will be tabulated by body system and preferred term with a breakdown by treatment. A subject with multiple adverse events within a body system is only counted once towards the total of this body system and treatment.

Serum total immunoglobulin G (IgG) and M (IgM)

Serum total IgG and IgM and percentage change from baseline will be listed by subject and visit/time. No descriptive summary statistics will be provided.

Immunogenicity

All immunogenicity results will be listed by subject and visit/time. No descriptive summary statistics will be provided.

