## 2.2 Secondary objective(s)

Objective(s)	Endpoint(s)
To evaluate the efficacy of IV CFZ533 using relevant MG related outcome measures throughout the 24 weeks treatment period	

• Mean Change from baseline in QMG Score and MGC Score.

• Proportion of patients with improvement by <math>\geq 3</math> points in QMG score.

• Proportion of patients with worsening by <math>\geq 3</math> points in QMG score.

• Proportion of patients intolerant to steroid taper.

• Proportion of patients who discontinued due to inefficacy or worsening.

To evaluate the decay in efficacy of IV CFZ533 using relevant MG related outcome measures throughout the 24 weeks follow-up period	
To evaluate changes in patient's quality of life (QOL) throughout the 24 weeks treatment period	Mean change from baseline in the MG-ADL and MG QOL-15.
To evaluate the PK of 2-hour IV infusion of CFZ533 at 10 mg/kg administered q4w for 6 doses	Free CFZ533 in plasma
To evaluate the PD of CFZ533 (CD40 saturation on B cells, extent/duration of target engagement)	Free CD40 on B cells, total CD40 on B cells and total soluble CD40 in plasma
To assess immunogenicity in CFZ533-treated patients and in placebo-treated patients (pre-existing anti-drug antibodies).	Quantitative analysis of anti-CFZ533 antibodies in plasma

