### **7.4 Study stopping rules**

As a guidance, dose limiting toxicities (DLTs) will be assessed according to the standardized toxicity grading scale.

The study will be placed on hold with no further dosing pending full safety review if *any* of the following criteria are met:

- One (1) patient with CFZ533-related death.
- Three (3) or more patients presenting with a serious adverse event that is related to CFZ533.
- One (1) patient presenting with CFZ533-related cytokine release syndrome.
- One (1) patient presenting with a CFZ533-related thromboembolic events that is at least of moderate severity.
- More than one (1) patient with a severe allergic reaction within the first 5 treated subjects or an incidence of >20% thereafter.
- Any treatment-related, severe adverse event considered drug related by the Investigator with the following exceptions:
  - Events not requiring treatment, and diagnostic procedures involving elective or non-urgent hospital admission,

- Disease Specific Events that are due to the patients underlying MG diagnosis,
- AEs/SAEs unrelated to the experimental compound as determined by the Investigator or Novartis.
- Two (2) or more patients presenting with:
  - Acute severe exacerbation of MG symptoms requiring hospitalization for treatment.
  - Progressive renal insufficiency or acute kidney injury defined as a moderate increase in serum creatinine (1.5 X ULN) in the setting of euvolemia at any time during the study related to CFZ53.
  - Emergent hypogammaglobulinemia defined as a reduction in total serum IgG or IgM concentration by 50% or more from baseline.
  - Severe systemic infection or opportunistic infection that requires treatment, e.g., sepsis, urosepsis, mycoses, pneumonia.
- Clinically significant (according to the Investigator), study drug-related persisting changes from baseline in vital signs, ECGs, or relevant persistent changes in laboratory parameters (not due to existing co-morbidities), in more than one (1) patient within the first 5 treated patients or an incidence of >20% thereafter.
- Other clinically significant changes or effects in the opinion of the Investigator or Sponsor that are deemed unsafe to continue dosing.

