### Clinical laboratory evaluations

All laboratory data will be listed by treatment, subject, and visit/time and if normal ranges are available abnormalities will be flagged. Summary statistics will be provided by treatment and visit/time.

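### The SAP rules out any summary of anti-drug antibodies (a secondary objective) and of serum IgG/IgM, and for IgG/IgM this departs from the protocol

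*SAP*

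**What the plan says.** **Objective.** Protocol 2.2 gives as a secondary objective "To assess immunogenicity in CFZ533-treated patients and in placebo-treated patients (pre-existing anti-drug antibodies", with the endpoint "Quantitative analysis of anti-CFZ533 antibodies in plasma". SAP 2.1.2 repeats the objective.

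**Immunogenicity in the SAP.** Section 8.1.1 names it as a safety variable. Section 8.1.2 then says: "All immunogenicity results will be listed by subject and visit/time. No descriptive summary statistics will be provided". It is not among the secondary variables in 7.2.1 or the plots in 7.2.5.

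**IgG/IgM in the SAP.** Section 8.1.2 says: "Serum total IgG and IgM and percentage change from baseline will be listed by subject and visit/time. No descriptive summary statistics will be provided".

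**Other laboratory data in the same SAP section.** These are arranged by arm in the listings, and then: "A separate listing is provided presenting all parameters in a subject with any abnormal values. Summary statistics will be provided by treatment and visit/time".

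**The protocol on laboratory data.** Section 8.4.4, Laboratory evaluations, includes serum total IgG and IgM. Section 11.5.2 says: "All laboratory data will be listed by treatment, subject, and visit/time and if normal ranges are available abnormalities will be flagged". It goes on to promise summary statistics by treatment and visit, with no visible exception for immunoglobulins.

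**Study hold.** Protocol 7.4 puts dosing on hold if two or more patients meet, among other criteria, "Emergent hypogammaglobulinemia defined as a reduction in total serum IgG or IgM concentration by 50% or more from baseline".

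**The concern.** These summaries have not simply been left to the table shells. The SAP states in words that they will not be produced, and does so twice. One of the two variables answers a secondary objective. The other is a marker the protocol itself chose to watch, for a drug that Protocol 3.6 expects to be immunosuppressive, in a trial whose first primary objective is safety.

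A randomised placebo arm lets background change be separated from drug effect. If the planned output is a patient-by-patient listing not described as arranged by treatment, the report has no planned place to say how many patients were ADA-positive, how many were positive before dosing, or how far immunoglobulins moved in each arm. Anyone wanting those figures would have to build them after unblinding, with definitions not fixed in advance.

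**Working it through.** The point rests on the text. The arithmetic only shows what the missing tables could deliver.

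**Step 1. Set the sections side by side.**

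| Data | Protocol | SAP listing described as by treatment | SAP summary by treatment |
|---|---|---|---|
| Vital signs, ECG | 11.5.2: summarised by treatment and visit | Yes (8.1.2) | Yes (8.1.2) |
| Clinical laboratory | 11.5.2: summarised by treatment and visit | Yes (8.1.2) | Yes (8.1.2) |
| IgG/IgM | 8.4.4: a laboratory evaluation, so 11.5.2 applies | No (8.1.2) | Ruled out (8.1.2) |
| ADA | 2.2: secondary objective; analysis text not visible | No (8.1.2) | Ruled out (8.1.2) |
| Trough levels of concomitant immunosuppressants | not compared here | Yes (SAP section 9) | None (SAP section 9) |

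The last row shows that withholding summaries does not require a listing without the arm. For IgG/IgM the SAP conflicts with the protocol. For ADA no conflict in analysis wording can be shown, because part of Protocol 11.5.2 is redacted; there the gap is between the stated objective and the planned output.

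**Step 2. Look for another output that fills the gap.**
- SAP 8.1.3 plans boxplots of laboratory parameters. It names neither IgG/IgM nor a split by arm, and ADA would not be covered.
- Adverse event tables are by treatment. Under Protocol 9.1, however, a laboratory change is an adverse event only if it causes symptoms, is judged clinically significant or needs therapy. A fall of 50% need not qualify, and an ADA-positive result need not appear either.

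**Step 3. Denominators.** Protocol 11.6 gives 36 evaluable patients, about 20% dropout and 44 randomised, 22 per arm. Check: 36 × 1.20 = 43.2, rounded up to 44, which reproduces the plan's figure. Dividing instead, 36 / 0.80 = 45. One patient makes no difference here.

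**Step 4. Precision of a by-arm count.** The counts below are illustrative, since the documents give no expected ADA rate or rate of immunoglobulin fall. Exact (Clopper-Pearson) 95% intervals at n = 22:

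| Count | Percent | 95% interval |
|---|---|---|
| 0/22 | 0 | 0 to 15.4 |
| 1/22 | 4.5 | 0.1 to 22.8 |
| 2/22 | 9.1 | 1.1 to 29.2 |
| 3/22 | 13.6 | 2.9 to 34.9 |

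For zero events the upper limit is 1 − 0.025^(1/22) = 0.154. With 18 per arm it is 1 − 0.025^(1/18) = 0.185.

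**Step 5. Why the tables should be descriptive.** For x events against none at 22 per arm, the two-sided Fisher p-value is 2 × C(22,x) / C(44,x):
- x = 2: 2 × 231 / 946 = 0.49
- x = 4: 2 × 7,315 / 135,751 = 0.108
- x = 5: 2 × 26,334 / 1,086,008 = 0.048

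Only a split of 5 to 0 or wider would fall below 0.05, so a test would add little.

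**The case against.** **The hold rule is already served.** A reader might infer that the study-hold criterion is left without the output it needs. The documents do not support that. The rule in Protocol 7.4 counts individual patients while the trial runs. The sponsor and investigator review blinded safety data on an ongoing basis, and under Protocol 6.5 and 10.3 a data monitoring committee receives unblinded data and oversees safety. A patient listing with percentage change suits such a count, so this objection stands in full.

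**The figures could be recovered.** A reader might also infer that the report could never give ADA incidence by arm. That goes too far. With 22 per arm, positives and large falls can be counted from the listings once treatment is known, and SAP 1.2 allows additional exploratory outputs through an addendum. The table shells in Module 7 are not available here. The objection narrows the point to what the plan commits to, but the two SAP sentences still direct that no summary be made.

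**No comparison was promised.** The objective is to assess immunogenicity, and placebo patients are mentioned in connection with pre-existing antibodies. That is right, and it argues for description without tests. Describing each arm is still part of assessing it.

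**Immunoglobulins are not a named primary safety endpoint.** Protocol 2.1 lists other measures, and Protocol 3.6 expects preformed antibody to persist. This limits how central the question is. It does not explain why IgG/IgM should be treated differently from other laboratory data.

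**Placebo samples.** The visible text does not confirm that post-baseline ADA samples from placebo patients are analysed. This stands, and the proposed table allows for it.

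**Conclusion.** The point holds in a limited form. SAP 8.1.2 excludes all descriptive summaries of a secondary-objective variable and of a laboratory variable that the protocol says will be summarised. As written, the planned outputs give no by-arm ADA incidence and no by-arm account of IgG/IgM change. For IgG/IgM the SAP and protocol disagree; for ADA the objective has no summarised answer.

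It should not be read as showing that the hold rule fails, that a between-arm test was owed, or that the data could not be counted afterwards. The primary efficacy analysis is unaffected.

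The conclusion assumes that IgG/IgM fall under the protocol's general statement on laboratory data, as their place in section 8.4.4 indicates, and that no unseen text reverses the two SAP sentences, which are unredacted and unqualified.

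**What to change.** In SAP 8.1.2, arrange both listings by treatment, patient and visit, and replace the two sentences that exclude summaries with the following, all descriptive and on the safety analysis set:

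1. **ADA:** number and percentage positive at baseline by arm; number and percentage with treatment-emergent ADA on CFZ533, and on placebo where post-baseline samples are analysed. State the denominator and the definition of treatment-emergent.
2. **IgG and IgM:** mean, SD, median, minimum and maximum of the value and of percentage change from baseline, by arm and visit, in line with other laboratory data; and number and percentage with a fall of 50% or more from baseline at any post-baseline visit, by arm. The 50% figure is the protocol's own, used here only as a reporting cut-off.

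If the sponsor prefers to keep IgG/IgM out of the laboratory summaries, the SAP should give the reason and record the departure from Protocol 11.5.2.

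**Cost:** two extra tables from data the SAP already plans to list, plus a text change before database lock. Trial conduct does not change. The drawback is imprecision at about 22 per arm, which exact intervals beside the percentages would make plain.
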